## List of Abbreviations

ACQ	Asthma Control Questionnaire
ADA	Anti-Drug Antibodies
ADCC	Antibody-dependent Cellular Cytotoxicity
AE	Adverse Event/Adverse Experience
AEC	Absolute Eosinophil Count
AER	Asthma Exacerbation Rate
AHR	Airway Hyperresponsiveness
APFS	Accessorized Prefilled Syringe
AR	Adverse Reaction
CBC	Complete Blood Count
CC	Clinical Center
CFR	Code of Federal Regulations
COPD	Chronic Obstructive Pulmonary Disease
CPT	Center Point Titer
CRF	Case Report Form
CRP	C-Reactive Protein
CRIMSON	Clinical Research Information Management System of the National Institute of Allergy and Infectious Diseases
CS	Corticosteroid
CSO	Clinical Safety Officer
CTCAE	Common Terminology Criteria for Adverse Events
DCR	Division of Clinical Research
DHHS	Department of Health and Human Services
DSMC	Data and Safety Monitoring Committee
ECG	Electrocardiogram
ePPND	enhanced pre- and post-natal development
ESR	Erythrocyte Sedimentation Rate
FDA	Food and Drug Administration
FEV	Forced Expiratory Volume
FIP1L1	Fip-1-like-1
FWA	Federal Wide Assurance
GCP	Good Clinical Practice
HCG	Human Chorionic Gonadotropin
HES	Hypereosinophilic Syndrome
HGB	Hemoglobin
HIV	Human Immunodeficiency Virus
IB	Investigator's Brochure
ICF	Informed Consent Form
ICH	International Conference on Harmonization
ID	Identification
IEC	Independent or Institutional Ethics Committee
IG	Immunoglobulin
IL	Interleukin

IL-5R	Interleukin 5 receptor
IND	Investigational New Drug
IRB	Institutional Review Board
ISM	Independent Safety Monitor
IUD	Intrauterine Device
IV	Intravenous
KLH	Keyhole Limpet Hemocyanin
LHES	Lymphocytic Variant Hypereosinophilic Syndrome
LPD	Laboratory of Parasitic Diseases
LVEF	Left Ventricular Ejection Fraction
MAb	Monoclonal Antibody
MRI	Magnetic Resonance Imaging
N	Number (typically refers to number of subjects/sample size)
NCI	National Cancer Institute, NIH
NIAID	National Institute of Allergy and Infectious Diseases
NIH	National Institutes of Health
NK	Natural Killer
NOAEL	No-Observed Adverse-Effect-Level
NYHA	New York Heart Association
OCRPRO	Office of Clinical Research Policy and Regulatory Operations
OHRP	Office for Human Research Protections
OHSRP	Office of Human Subjects Research Program
OTC	Over-the-Counter
PBMC	Peripheral Blood Mononuclear Cells
PDGFRA	Platelet-derived growth factor receptor alpha
PHI	Protected Health Information
PI	Principal Investigator
PK	Pharmacokinetics
PT	Prothrombin Time
PTT	Partial Thromboplastin Time
QA	Quality Assurance
QC	Quality Control
RBC	Red Blood Cell Count
RCHSPP	Regulatory Compliance and Human Subjects Protection Program
SAE	Serious Adverse Event/Serious Adverse Experience
SAR	Serious Adverse Reaction
SC	Subcutaneous
SD	Standard Deviation
SMC	Safety Monitoring Committee
SMM	Sponsor Medical Monitor
SOP	Standard Operating Procedure
SRCP	Safety Review and Communications Plan
SUSAR	Suspected and Unexpected Serious Adverse Reaction
TARC	Thymus and activation-regulated chemokine
Tdap	Tetanus-diphtheria-acellular pertussis
Th2	T helper 2

TCR	Tissue cross-reactivity
TEAE	Treatment-Emergent Adverse Events
TK	Toxicokinetics
UP	Unanticipated Problem
UPnonAE	Unanticipated Problem that is not an Adverse Event

## Protocol Summary

Full Title:	A Phase 2 Randomized, Double-Blind, Placebo-Controlled Study to Evaluate the Safety and Efficacy of Subcutaneous (sc) Benralizumab in Reducing Eosinophilia in Subjects with Hypereosinophilic syndrome (HES)
Short Title:	Benralizumab for treatment-refractory HES
Clinical Phase:	2
IND Sponsor:	OCRPRO/NIAID/NIH
Conducted by:	NIAID/LPD
Principal Investigator:	[name]
Sample Size:	N=20
Accrual Ceiling:	N=25
Study Population:	Adult subjects aged 18-75 with PDGFRA -negative HES who are symptomatic with AEC >1000/ $\mu$ L on stable HES therapy for at least 1 month
Accrual Period:	2 years
Study Design:	This will be a randomized, placebo-controlled, double-blind study followed by an open-label extension. A maximum of 20 subjects will be randomized (1:1) to receive sc injections of 30 mg of benralizumab or placebo at 0, 4 and 8 weeks. Eosinophil counts for a subject will be blinded and background HES therapy will not be tapered until that subject has reached 13 weeks on study. Beginning at the 12 week visit, all subjects will receive open-label benralizumab (30 mg sc) every 4 weeks for 3 doses. Subjects with an AEC<1000/ $\mu$ L and improvement in clinical symptoms without an increase in background HES therapy (responders) at the 24 week visit will continue to receive benralizumab every 4 weeks for the duration of the study (1 year). Non-responders will not receive additional doses of benralizumab. Following the initial dose of benralizumab or placebo and the first open-label (at 12 weeks) dose of benralizumab, subjects will be followed daily for 3 days, weekly for 4 weeks, and every 2 weeks for 8 weeks. Subsequent visits will be at 4 weeks intervals for responders and at 12 week intervals for non-responders for the duration of the study. For subjects who complete the study and for whom benralizumab provides sustained clinical benefit, drug may be provided on an open-label extension. After 2 years of stable and complete response to benralizumab, the dosing interval may be increased to every 8 weeks. Subjects will receive diphtheria-

tetanus-acellular pertussis (Tdap) booster immunization at the 22 week visit. Titers will be measured 6 weeks after immunization. Subjects with a sustained and complete response to benralizumab with a stable dose for another 2 years will be transitioned to the FasentraPEN autoinjector for at-home self-administration (or by a local provider), with monthly blood counts and visits to the NIH once every 6 months.

**Study Duration:** Start Date: March 2014 End Date: June 2025  
Subjects will be on study for 12 months (or longer if enrolled on the open label extension).

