## Précis

Hypereosinophilic syndrome (HES) is a rare group of heterogeneous disorders characterized by marked peripheral eosinophilia ( $>1500/\mu\text{L}$ ) and evidence of eosinophil-associated tissue damage. Although a high proportion of patients respond initially to corticosteroid therapy, high doses are often necessary to control the eosinophilia and clinical symptoms, and many patients become relatively refractory to therapy and/or develop serious side effects. IL-5 receptor  $\alpha$  (IL-5R $\alpha$ ) expression in humans is restricted to eosinophils, basophils, mast cells and their precursors and is, therefore, an ideal target for the therapy of HES. Benralizumab was approved in the US in 2017 for treatment of severe asthma in patients 12 years or older and with eosinophilic phenotype. The product has a well-established safety profile based on several years of post-market experience for severe asthma since its approval. In order to explore the safety and efficacy of benralizumab in the treatment of HES, 20 adults (men and non-pregnant women, 18-75 years of age) with HES who are symptomatic with AEC  $>1000/\mu\text{L}$  on stable HES therapy for at least 1 month will be recruited for this randomized, placebo-controlled, double-blind phase 2 trial. Benralizumab (30 mg) or placebo will be administered sc at weeks 0, 4, and 8. Eosinophil counts will be blinded for a subject and background HES therapy will not be tapered until that subject has been on study for 13 weeks. At weeks 12, 16, and 20, all subjects will receive a sc injection of benralizumab. Subjects demonstrating a response at the 24 week visit (eosinophil count  $<1000/\mu\text{L}$  and stable or improved clinical symptoms without an increase in background HES therapy) will continue to receive additional 30 mg sc injections every 4 weeks. Following the initial dose of benralizumab or placebo and the first open-label dose of benralizumab, subjects will be followed daily for 3 days, weekly for 4 weeks, and every 2 weeks for 8 weeks. Subsequent visits will be at 4 weeks intervals for responders and 12 weeks intervals for non-responders for a minimum of two years. Subjects with stable and complete response for  $\geq 2$  years may be eligible to receive benralizumab at a dosing interval of every 8 weeks. Subjects will receive diphtheria-tetanus-acellular pertussis (Tdap) booster immunization at the 22 week visit. Titers will be measured 6 weeks after immunization. The primary endpoint of the study is a 50% reduction in peripheral blood eosinophilia on stable background therapy at 12 weeks post-initiation of study drug. Secondary endpoints will include absolute eosinophil count, the frequency and severity of adverse events, reduction in signs and symptoms of HES, tissue eosinophilia, numbers of eosinophils, mast cells and their precursors in bone marrow, levels of markers of eosinophil and mast cell activation, eosinophil count and background HES therapy at 1 year, pharmacokinetics and anti-drug antibody (ADA) levels and eosinophil count after 24 weeks of every 8 week dosing. Exploratory endpoints will address predictors of response to benralizumab and the impact of eosinophil depletion on vaccine responses and glucose homeostasis. Subjects who complete the study and for whom benralizumab provides sustained clinical benefit, may be eligible to receive drug on an open-label extension protocol until regulatory approval and commercial availability of the marketed drug to prescribing physicians (for any indication), or until development of benralizumab is discontinued by AstraZeneca.

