## 3 Study Design

### 3.1 Description of the Study Design

This study will be a single center trial with 5 parts: 1) randomized, double-blind sc benralizumab vs. placebo every 4 weeks for 12 weeks, 2) open-label sc benralizumab every 4 weeks for 12-36 weeks, 3) open-label sc benralizumab extension for benralizumab responders, with doses every 4 weeks for 6 months, 4) open label substudy of sc benralizumab administration every 8 weeks in complete responders, and 5) open-label extension of self-administered sc benralizumab using an autoinjector for subjects with a sustained and complete response, for a minimum of 2 years. Eligible subjects enrolled on study protocol 94-I-0079 (Activation and function of eosinophils in conditions with blood or tissue eosinophilia) or referred from outside physicians for evaluation of hypereosinophilia will be invited to participate. A maximum of 20 subjects will be enrolled.

Baseline evaluation will include a complete history and physical examination, routine laboratory testing and assessment of end organ involvement (see [Appendix A](#)). Baseline research studies will include bone marrow aspirate and biopsy to assess eosinophil and mast cell numbers and activation, storage of peripheral blood mononuclear cells (PBMC) for future studies, assessment of baseline eosinophil activation and T/B/NK subsets by flow cytometry, and measurement of serum markers of eosinophil and mast cell activation. Potential predictors of response to benralizumab, including eosinophil surface and soluble IL-5R $\alpha$  levels and plasma cytokine profiles, will also be explored.

Part 1: Benralizumab (30 mg) or placebo will be administered sc every 4 weeks for 3 doses (at weeks 0, 4 and 8). Eosinophil counts will be blinded during this time and background HES therapy will not be tapered.

Part 2: Following the placebo-controlled portion of the trial, all subjects will receive an sc injection of benralizumab at weeks 12, 16, and 20. Eosinophil counts will be unblinded after the first week of open-label therapy (study week 13) and HES therapy may be tapered if clinically indicated. Subjects demonstrating a response at the 24 week visit (eosinophil count <1000/ $\mu$ L and stable or improved clinical symptoms without an increase in background HES therapy) will receive additional 30 mg sc injections every 4 weeks for 6 doses. Non-responders will receive no further doses of benralizumab.

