Appendix F: FASENRA PEN: Instructions for Use).

### **5.3.2 Study Drug Dosing**

Population modelling of clinical efficacy endpoints (Asthma Exacerbation Rate (AER), Asthma Control Questionnaire (ACQ), and Forced Expiratory Volume in 1 second (FEV1)) from the interim analysis for the Phase 2 asthma study, MI-CP220, and stochastic simulations identified the optimal dose and regimen for the pivotal Phase 3 studies with benralizumab in adult subjects with asthma as 30 mg every 4 weeks for 3 doses then every 8 weeks thereafter. This dosing regimen corresponds to the ED90 for AER and ACQ, and maintains a steady-state PK exposure close to EC90 levels for FEV1 and ACQ. With a steady-state PK exposure 50% higher than 20 mg every 8 weeks, the 30 mg dose every 8 weeks is expected to reduce the impact of PK variability related to factors such as higher body weight. The incidence of ADA (especially high-titer ADA) and the impact on PKPD were dose-dependent with decreased incidence and impact at higher doses. However, the ADA response was not more frequent in those subjects with blood eosinophils  $\geq 300$  cells/ $\mu$ L (20.7%) as compared to those with blood eosinophils  $< 300$  cells/ $\mu$ L (21.7%). Since doses higher than 20 mg are expected to reduce the impact of ADA without modifying the dose interval, and there are no identified safety risks that would warrant consideration of a lower dose, subjects will receive 30 mg every 4 weeks for 3-12 doses depending on whether they receive drug or placebo during the first part of the study and whether they demonstrate a clinical and hematologic response at study week 24.

Subjects who complete the study and for whom benralizumab appears to provide a sustained clinical benefit, may be eligible to receive drug under an open-label extension until regulatory approval and commercial availability of the marketed drug to prescribing physicians (for HES), or until AstraZeneca ceases development of benralizumab for this indication. Complete responders may be eligible to extend the dosing interval to every 8 weeks after sustained and complete remission of eosinophilia for  $\geq 2$  years at the investigator's discretion.

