## **6.4 Study Phase**

Within 14 days of completion of baseline studies, subjects will begin treatment with study drug.

Benralizumab (30 mg) or placebo will be administered sc (as described in Section 5.4) in the OP11 clinic, the 5 SW Day Hospital, or the 5 SE inpatient nursing unit. Vital signs will be checked immediately prior to and at 30 minutes after the injection.

Subjects will be admitted to the inpatient ward for overnight observation following the first dose of study drug to facilitate monitoring of AEs. The inpatient stay may be extended if clinically indicated. Subjects will be seen daily (in OP11 or on the inpatient ward) for 3 days following the first dose of study drug, and then at weeks 1, 2, 3, 4, 6, 8, 10, and 12. Re-dosing of benralizumab or placebo will occur every 4 weeks for a total of 3 doses (at weeks 0, 4, and 8). Subjects who develop AEs after the first dose of study drug may be monitored during subsequent doses at the discretion of the investigator. Subjects who develop grade 3 or greater AEs that are considered by the investigator to be possibly, probably, or definitely related to study drug will promptly, and prior to subsequent dosing, be discussed in writing or verbally with a Sponsor Medical Monitor in the Clinical Safety Office.

At the 12 week visit, all subjects will receive benralizumab (30 mg) sc. Since the subjects who received placebo during the first 12 weeks of the study will be receiving their first dose of benralizumab at this visit, all subjects will be admitted to the inpatient ward for overnight observation following the first dose of study drug and followed daily (in OP11 or on the inpatient ward) for 3 days, every week for 4 weeks and then at weeks 1, 2, 3, 4, 6, 8, 10, and 12, 13, 14, and 15. Re-dosing of open-label benralizumab will occur every 4 weeks for a total of 3 doses (at weeks 12, 16 and 20), after which subjects demonstrating a clinical response will continue to receive additional doses every 4 weeks for one year. Non-responders will receive no further doses of benralizumab. Subsequent visits will occur at 4-week intervals for responders and at 12-week intervals for non-responders for the duration of the study. After a minimum of 2 years of complete response on the open-label extension, the dosing interval (and visits) may be increased to every 8 weeks (the FDA-approved dosing interval for severe eosinophilic asthma).

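### The week-24 continuation rule requires improved symptoms in the Protocol Summary but accepts stable ones in the Précis and Section 3.1, so a stable subject gets 0 or 6 further doses; the extension-end wording also conflicts

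*Combined protocol and SAP*

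**What the plan says.** **Week-24 rule.** All three full statements require AEC below 1000/µL and no increase in background HES therapy. They differ on symptoms.

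- Protocol Summary, Study Design: "and improvement in clinical symptoms without an increase in background HES therapy (responders) at the 24 week visit will continue to receive benralizumab".
- Précis: "and stable or improved clinical symptoms without an increase in background HES therapy) will continue to receive additional 30 mg sc injections every 4 weeks".
- Section 3.1, Part 2: "stable or improved clinical symptoms without an increase in background HES therapy) will receive additional 30 mg sc injections every 4 weeks for 6 doses".

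The Summary gives the consequence of failing the rule: "Non-responders will not receive additional doses of benralizumab". It also ties follow-up to the classification: "Subsequent visits will be at 4 weeks intervals for responders and at 12 week intervals for non-responders for the duration of the study".

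Two other sections mention the decision without defining its symptom part. Section 5.3.2 states that "subjects will receive 30 mg every 4 weeks for 3-12 doses", depending on the randomized arm and on "whether they demonstrate a clinical and hematologic response at study week 24". Section 6.4 says of the three open-label doses: "after which subjects demonstrating a clinical response will continue to receive additional doses every 4 weeks for one year".

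**End of the open-label extension.** The Précis ends supply when the drug is approved and commercially available for any indication, or when its development is discontinued. Sections 3.1 (Part 3), 5.3.2 and 6.7 tie both conditions to HES.

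**Minor points.** The opening list in Section 3.1 gives part 3 a length of 6 months. The Part 3 paragraph runs it until availability for HES, and Part 4 requires at least 2 years on the extension. For the autoinjector, the Summary and Section 3.1 (Part 5) say that qualifying subjects will be moved to it, while Sections 6.4 and 6.7 say that they may be eligible. The Summary asks for another 2 years on a stable dose; Section 3.1 asks for a minimum of 2 years.

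**The concern.** The contested state is foreseeable. Section 4.3 requires signs or symptoms at entry, and Section 3.1 allows background therapy to be tapered from week 13. A subject can reach week 24 with a low count, unchanged symptoms, and the same or less background therapy. The Summary calls that subject a non-responder; the Précis and Section 3.1 call the same subject a responder.

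The label decides whether drug continues and how often the subject is seen. It also decides what the week-48 secondary endpoint in Section 3.2.2 (eosinophil count and background HES therapy) measures: a subject still on monthly drug, or one who stopped at week 20. The long-term safety and efficacy data inherit the same ambiguity.

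The extension wording matters because the Précis itself records the 2017 asthma approval and several years of post-market experience. Read literally, its end condition already looks met, while the other sections continue supply.

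**Working it through.** **1. The plan's own dose counts.**

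- Blinded doses: weeks 0, 4, 8 = 3.
- Open-label doses for all: weeks 12, 16, 20 = 3.
- Conditional doses: weeks 24, 28, 32, 36, 40, 44, that is (44 − 24)/4 + 1 = 6. This matches the six in Section 3.1. It also matches the 12-36 week open-label period in Sections 3.1 and 13.4, since (36 − 12)/4 = 6, and the marked drug-administration columns in Appendix B (weeks 24, 28, 32, 36, and 40/44 together).
- Minimum total: 0 + 3 = 3 (placebo arm, non-responder). Maximum: 3 + 3 + 6 = 12 (benralizumab arm, responder). This reproduces the 3-12 range in Section 5.3.2.

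**2. The contested subject** (AEC below 1000/µL, stable symptoms, no increase in background therapy).

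| | Protocol Summary | Précis and Section 3.1 |
|---|---|---|
| Symptom condition | improved | stable or improved |
| Classification | non-responder | responder |
| Further doses | 0 | 6 (number from 3.1) |
| Total, benralizumab arm | 3 + 3 = 6 | 3 + 3 + 6 = 12 |
| Total, placebo arm | 0 + 3 = 3 | 0 + 3 + 6 = 9 |
| Last dose | week 20 | week 44 |
| Last dose to week 48 | 48 − 20 = 28 weeks | 48 − 44 = 4 weeks |
| Visits after week 24 | weeks 36, 48 (2) | weeks 28 to 48, 4-weekly (6) |

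The tetanus titer at week 28 (Section 6.5, Appendix D) may add one visit in the left column.

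**3. Does another section settle it?** Sections 5.3.2 and 6.4 refer to a response but do not say whether stable symptoms qualify. The conditional doses in Appendix B carry footnote 3, whose text was not in the copy available to this review. It could show which rule was meant to operate, but it could not remove the difference between the Summary and Section 3.1.

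**4. Reach into the analysis.** The primary endpoint is read at week 12 and the rule acts at week 24. Sections 13.3 and 13.4 specify no analysis by week-24 response. Exact enumeration of the one-sided Fisher test at 2.5% with a 1% placebo rate reproduces all 15 entries of Table 2 (for example 79.0% at 60% responders with 10 per group). None of its inputs involves the rule.

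**5. Extension end.** For a drug approved in asthma, with no HES approval mentioned in the documents, the any-indication condition and the HES condition give opposite answers. Three sections agree on HES; the Précis stands alone.

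**The case against.** The strongest case is that little now depends on this. Accrual was planned from March 2014 for 2 years, which puts the last entry in March 2016 and the last week-24 visit 168 days later, in about August-September 2016. The current text cites the 2017 approval, so on that plan every week-24 decision predates it. Appendix D already reports reactions after the first open-label dose. Doses given are recorded under Sections 5.4 and 15.1, so actual exposure can be recovered. The extension conflict is a single phrase in the Précis.

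Much of this stands, and it limits the weight of the point. It does not remove it. Dose records show what was given, not which definition classified the subject. Actual accrual dates are not in the documents. The extension and autoinjector rules can operate until the listed end in June 2025.

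Some stronger readings are tempting but unsupported:

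- A reader might take the one-year phrase in Section 6.4 as a further year of dosing from week 24. The Summary (to the end of the 1-year study), Section 3.1, the 12-dose maximum in 5.3.2, Section 13.4 and Appendix B all exclude that. It needs only clearer wording.
- A reader might date the extension conflict from the November 2017 approval. This version is later: it cites several years of post-market experience and reproduces instructions marked 2019. Earlier protocol text is not available, so no duration can be given.
- A reader might infer that the Summary doubles the autoinjector qualifying period. That depends on what the additional 2 years follow, and the text does not say. It is an ambiguity without a size.
- Section 5.1.1 permits use of the pen after training. It is not an eligibility rule and adds nothing to the will-versus-may conflict.

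**Conclusion.** The concern holds as a contradiction in the text. Under otherwise identical conditions, the Summary and Section 3.1 direct opposite treatment and follow-up for the same subject from week 24 to week 48, with the differences tabulated above. Those figures assume that scheduled doses are given on time and that the six doses in Section 3.1 apply to responders.

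Confidence is high that the passages conflict. It is lower on whether any part of the protocol shows the intended rule, because the Appendix B footnote could not be read. How many of the 20 subjects are affected cannot be derived from the documents. A reader might infer that the efficacy conclusion is at risk; it is not, because the primary comparison is complete before the rule acts.

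The extension-end conflict is equally plain and may still bear on drug supply. The length of part 3 and the autoinjector wording are minor. The whole point deserves correction, but ranks below anything that affects the primary analysis.

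**What to change.** - Bring the Protocol Summary, the Précis and Section 3.1 to one week-24 response definition. Align Sections 5.3.2 and 6.4 with it, and Appendix B footnote 3 if it states the rule. Clarify the one-year phrase in 6.4 in the same edit.
- Reconcile the extension-end condition in the Précis with Sections 3.1, 5.3.2 and 6.7.
- Reconcile the two lengths of part 3 within Section 3.1.
- Reconcile the autoinjector qualifying period (Summary, 3.1) and whether the step is mandatory or optional (Summary and 3.1 against 6.4 and 6.7).
- If week-24 decisions have already been made, record which definition was applied to each subject. State it with any week-48 or long-term result reported by responder status.

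Which wording stands is for the sponsor to decide. The cost is amendment wording and one record of past decisions; sample size, testing and data collection do not change.
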